3.5 Termination or Suspension of Investigational Sites

A study site may be terminated prematurely or suspended if the site (including the Investigator) is found to be in significant violation of GCP, the protocol, or the contractual agreement, or is unable to ensure adequate performance of the study, or for reasons as otherwise permitted by the contractual agreement.

3.6 Conditions for Individual Subject Discontinuation of Study Drug or Withdrawal from the Study

[figure not shown]
The primary reason for permanent discontinuation of a subject from the study drug should be recorded in the electronic Case Report Form (eCRF). Individual subjects may be discontinued from the study drug in the following circumstances:

1. Concurrent enrolment in other clinical studies involving investigational products or enrolment in other types of clinical research judged not to be scientifically or medically compatible with this study.
2. Use of a prohibited concomitant medication.
3. Major protocol deviation e.g., the discovery after administration of the first dose of study medication that the subject failed to meet protocol entry criteria or did not adhere to protocol requirements, and continued participation poses an unacceptable risk to the subject’s health or undermines the ability to achieve the objectives of the study.

4. Lost to follow-up. The subject did not return to the study center and attempts to contact the subject were unsuccessful. Attempts to contact the subject must be documented.
5. Evidence of pregnancy during the treatment period of the study.
6. Clinically significant changes from baseline in ECG recordings considered treatment-related including an increase from baseline in heart rate corrected QT interval using Fridericia's formula (QTcF) to a value of ≥ 500 millisecond (msec). Single ECGs should be repeated at 5-minute intervals, 3 times, to confirm any increased QTcF interval values. In the event of an increased QTcF interval of ≥ 500 msec, the subject must be monitored until the value returns to below 500 msec.
7. Clinically significant muscle injury including test abnormalities (e.g., CK) as defined in [Section 3.7.1](#).
8. Clinically significant liver toxicity including test abnormalities (e.g., ALT/AST) as defined in [Section 3.7.2](#).
9. Clinically significant kidney toxicity including test abnormalities (e.g., creatinine levels) as defined in [Section 3.7.3](#).

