3.9 Temporary Discontinuations

Subjects may be temporarily discontinued from study drug while AEs and/or laboratory test abnormalities are being investigated and/or at the request of the Medical Monitor. The Investigator should discuss with the Medical Monitor and Sponsor any subject for whom temporary or permanent discontinuation of study drug is being considered.

If a subject misses several consecutive doses due to personal circumstances or due to an AE not related to study drug, they may be allowed to restart dosing after discussion between the Investigator, Medical Monitor and Sponsor (See [Section 5.9](#)).

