6.5 Weeks 8, 16 and 20 (Days 56, 112 and 140)

Subjects who are WOCBP at risk of pregnancy will be supplied with urine pregnancy tests to use at home at Weeks 8, 16 and 20. Study Center staff will need to contact the subjects by telephone to obtain the result of the pregnancy test and enter the result into the eCRF. Subjects may be given a reminder telephone call to conduct the test if necessary.

6.6 Weeks 12 and 24 (Days 84 and 168): Visits 5 and 7

Site staff will need to provide subjects with meals and snacks at appropriate times during the visit to ensure subjects have enough energy prior to completing the exercise tests.

Subjects will attend the Study Center on Days 84 and 168. On these days, the subject will take their daily dose in the Study Center. The following assessments will be carried out:

- Obtain second morning void urine sample for:
 - Bone marker - NTX
 - Urinalysis
 - Drugs of abuse
 - Urine for pregnancy testing (WOCBP only)
- Obtain blood samples for:
 - Hematology (including HbA1c at Week 24 only)
 - Biochemistry
 - Additional bone and calcium metabolism markers
 - Pre-dose plasma sample for pharmacokinetic analysis of REN001
- Administer the study drug with food under supervision of clinical staff and the time of dosing recorded.
- Review concomitant medications, non-drug treatments and study medication compliance
- Review of adverse events
- Physician completion of subjects PMM phenotypic description (Week 24 only)
- Review of pedometer eDiary data
- Brief physical examination (including weight)
- 12-lead ECG
- Vital signs (including temperature)
- Obtain plasma samples for pharmacokinetic analysis of REN001 (1, 2, 3 and 4* hours postdose)
- Review of last 7 days pedometer data
- MFIS
- BPI
- SF-36
- PGIS – muscle symptoms

- PGIS – fatigue symptoms
- PGIC – muscle symptoms (Week 24 only)
- PGIC – fatigue symptoms (Week 24 only)
- PROMIS Short Form – FACIT Fatigue 13a
- WPAI:SHP
- 12MWT
- 30STS
- Capsule counts of remaining capsules including any opened IMP bottles
- Subjects will be provided with a urine collection cup and instructions for collecting a second morning void at the Week 24 visit if they are unable to do this at the Study Center for any reason (Week 12 only)
- Eye examinations (may be completed \pm 14 days of the visit if required)

Assessments should be conducted to ensure that the PRO questionnaires are completed prior to exercise testing and the 12MWT must be done at least 1 hour before the 30STS.

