6.9 Subject Continuation In Study Off IMP

If a subject discontinues taking study drug, they will be strongly encouraged to continue in the study for their Week 12 and Week 24 visits (see [Figure 3](#)). If they agree to remain in the study off-IMP as a minimum they will be requested to complete the following assessments:

- Review concomitant medications and non-drug treatments
- Review of adverse events

- Vital signs (including temperature)
- MFIS
- 12MWT

Table 2: Schedule of Activities

Time and Events Table	Screening	Baseline ^{1, 2} (Day 1)	Week 2 ³ (Day 14)	Week 4 ³ (Day 28)	Week 8 (Day 56)	Week 12 ^{2, 4} (Day 84)	Week 16 (Day 112)	Week 18 ³ (Day 126)	Week 20 (Day 140)	Week 24 ^{2, 4} (Day 168).	Early Term ^{2, 5}	Follow Up ³ (21-28 days post last dose)
Visit number	1	2	3	4		5		6		7		8
Window (days)			±3	±3		±7		±7		±7		
Informed Consent	X											
Completion of Proforma and data entered into eCRF ⁶	X											
Demographics	X											
Medical/medication/drug/alcohol/tobacco history ⁷	X											
Physician completion of PMM phenotypic description		X								X	X	
Physical exam ⁸	X	X				X				X	X	
12-lead ECG	X	X				X				X	X	
Supine Vital signs (BP, PR and temperature)	X	X	X	X		X		X		X	X	X
Serum FSH ⁹	X											
HbA1c	X									X	X	
Hepatitis B/C/HIV	X											
Safety labs (inc. urinalysis)	X	X ¹⁰	X	X		X		X		X ¹¹	X	X ¹¹
Blood sample for bone and calcium markers		X				X				X	X	
Pregnancy Test (WOCBP only) ¹²	X	X		X	X	X	X		X	X	X	X
Blood sample for genotyping ¹³	X											
Population PK blood sample ¹⁴		X	X	X		X		X		X	X	
Urine drugs of abuse	X	X				X				X	X	
Urine NTX		X				X				X	X	

Time and Events Table	Screening	Baseline ^{1, 2} (Day 1)	Week 2 ³ (Day 14)	Week 4 ³ (Day 28)	Week 8 (Day 56)	Week 12 ^{2, 4} (Day 84)	Week 16 (Day 112)	Week 18 ³ (Day 126)	Week 20 (Day 140)	Week 24 ^{2, 4} (Day 168).	Early Term ^{n-2, 5}	Follow Up ³ (21-28 days post last dose)
Sites to provide appropriate snacks and lunch	X	X				X				X	X	
Pedometer eDiary data collection (inc. review)	X	X ¹⁵		X		X		X		X		
MFIS / PGIS (muscle symptoms), PGIS (fatigue symptoms) and PROMIS – Short form FACIT fatigue 13a	X	X		X		X		X		X	X	
SF-36 / BPI and WPAI:SHP		X		X		X		X		X	X	
PGIC (muscle symptoms) and PGIC (fatigue symptoms)										X	X	
12 Minute Walk Test	X ¹⁶	X				X				X	X	
30STS		X				X				X	X	
IMP Capsule Counts			X	X		X		X		X	X	
Eye examination	X ¹⁷					X				X	X	
Wrist radiograph	X ¹⁸											
Concomitant medication review	X-----X											

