7.1.8 Electrocardiogram Recording

Single ECG measurements using a 12-lead ECG machine will be taken after the subject has rested for at least 10 minutes in a supine position. To ensure safety of the subjects, a qualified individual at the site will evaluate all ECGs.

If the QTcF is ≥ 450 msec at Screening or QTcF is ≥ 500 msec for any post-baseline ECG, the ECG intervals should be inspected carefully to ensure that the RR interval has been recorded correctly, and a single ECG will be repeated at 5-minute intervals 3 times. If these values are consistently high (≥ 450 or 500 msec, respectively), or if the Investigator or Medical Monitor has any concern, as a precautionary measure, the subject will be screen failed or discontinue study treatment as appropriate (see [Section 3.6](#)).

If a machine read QTcF value is prolonged, as defined above, repeat measurements may not be necessary, provided a qualified physician's interpretation determines that the QTcF values are acceptable for the individual. In some cases, it may be necessary to repeat abnormal ECGs to rule out improper lead placement as contributing to the ECG abnormality. It is important that leads are placed in the same positions each time in order to achieve precise ECG recordings.

ECGs may be sent to an ECG vendor for centralized reading at a later date if deemed necessary.

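### Protocol 3.6 and 7.1.8 do not make clear whether study drug must stop at a confirmed QTcF of 500 msec or more that is judged unrelated to treatment

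*Protocol*

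**What the plan says.** Protocol Section 3.6 opens its list with "Individual subjects may be discontinued from the study drug in the following circumstances". Item 6 of that list is "Clinically significant changes from baseline in ECG recordings considered treatment-related including an increase from baseline in heart rate corrected QT interval", Fridericia-corrected, to 500 msec or more. Three repeat ECGs at 5-minute intervals confirm the value, and "the subject must be monitored until the value returns to below 500 msec".

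Protocol Section 7.1.8 applies the same 500 msec limit to any post-baseline ECG, with the same three repeats. It then gives the action for values that stay high, or that worry the Investigator or the Medical Monitor for any reason. The action reads: "as a precautionary measure, the subject will be screen failed or discontinue study treatment as appropriate". The sentence ends with a reference to Section 3.6. Repeats may be skipped for a machine-read value when a qualified physician "determines that the QTcF values are acceptable for the individual".

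For the ECG schedule, Section 6.6 says "Subjects will attend the Study Center on Days 84 and 168". Table 2 places the 12-lead ECG at Screening, Baseline, Week 12, Week 24 and Early Termination, with none at Weeks 2, 4 or 18. The Baseline ECG is taken before the first dose.

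**The concern.** The two sections describe the same confirmed finding but word the trigger for stopping drug differently. Section 3.6 adds a judgement of relatedness and is permissive. Section 7.1.8 asks for no such judgement and is phrased as an instruction, softened by *as appropriate*. The case that falls between them is a confirmed QTcF of 500 msec or more that the investigator attributes to something other than study drug.

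That attribution is made without knowing the allocation (Section 5.3). It is also made in a disease where exclusion criterion 14 describes some conduction abnormalities as common, so attributing an ECG change to the disease is foreseeable. With at least 35 centers, some could read Section 3.6 as leaving the stop to their discretion while others stop under Section 7.1.8. What is at stake is the clarity of a cardiac safety rule for the individual subject.

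**Working it through.** No figure in the plan needs reproducing. The check is a comparison of the two texts, followed by the interval between scheduled ECGs.

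**Step 1. The two rules side by side**

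| Element | Section 3.6 item 6 | Section 7.1.8 |
|---|---|---|
| Threshold | QTcF ≥ 500 msec | QTcF ≥ 500 msec |
| Confirmation | 3 repeats, 5 minutes apart | 3 repeats, 5 minutes apart |
| Causality | within changes *considered treatment-related* | not mentioned |
| Force | *may* | *will*, with *as appropriate* |
| Other trigger | none in this item | any concern of Investigator or Medical Monitor |
| Cross-reference | none to 7.1.8 | to 3.6 |

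Threshold and confirmation agree. Causality and force do not.

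**Step 2. Can the two be read as one rule?** There are two candidate readings, and they point in opposite directions.
- In item 6, *including* could mean that a rise to 500 msec or more qualifies in itself. Causality then drops out and the sections agree that drug stops. In the sentence as written, however, the QTcF rise sits inside the treatment-related changes.
- In 7.1.8, *as appropriate* with the reference to 3.6 could import the relatedness condition, in which case a precautionary rule waits on attribution. It could also simply sort screen failure from discontinuation.

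Neither reading is excluded by the text, so the rule is ambiguous.

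**Step 3. Does another section settle it?**
- Section 3.6 item 10 (a treatment-emergent event that could cause significant impairment) has no causality condition and permits a stop. It does not mention QTcF.
- Section 3.9 permits temporary stops and asks for discussion with the Medical Monitor and Sponsor. It gives no QTcF rule.
- Protocol Section 8.6 and SAP Section 12.5 flag 500 msec or more whatever the cause. These are reporting rules and do not govern dosing.

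None says which condition applies to a confirmed value judged unrelated.

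**Step 4. Interval to the next scheduled ECG.** Inputs from Table 2: Week 12 = Day 84, Week 24 = Day 168, window ±7 days for each.
- Nominal: 168 − 84 = 84 days, and 84/168 = 50% of the treatment period.
- Shortest: (168 − 7) − (84 + 7) = 161 − 91 = 70 days.
- Longest: (168 + 7) − (84 − 7) = 175 − 77 = 98 days.

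Dosing ends at Week 24, so Week 12 is the only scheduled on-treatment ECG at which a stop changes exposure in this study.

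**The case against.** The strongest reply is that there is no real conflict. Section 3.6 is a permissive list. It does not claim to be exclusive, and it nowhere authorises continued dosing at a confirmed value of 500 msec or more. Section 7.1.8 is the specific ECG instruction, and a site that stops under it breaches nothing in Section 3.6. The Section 3.6 list also opens with the reason for permanent discontinuation, whereas the step in Section 7.1.8 is precautionary. Section 3.9 asks the Investigator to discuss with the Medical Monitor and Sponsor any subject being considered for a stop, which narrows differences between sites. A clinically significant ECG change is an adverse event (Section 7.1.1.2) and is followed whatever its cause (Section 7.1.1.11).

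Most of this stands. It rules out two stronger readings that a reader might infer. One is that the protocol contradicts itself outright or directs sites to keep dosing. It does neither, because a site that continued would be relying on the permissive wording and the cross-reference. The other is that a subject could go 84 days unmonitored above 500 msec. The 84 days is only the gap between scheduled ECGs: item 6 requires monitoring until the value falls below 500 msec, and adverse event follow-up runs alongside it.

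What the reply does not do is show which condition governs. Discussion under Section 3.9 is prompted when a stop is being considered, and that is the decision the two sections word differently.

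**Conclusion.** The point holds as an ambiguity in a safety rule. Confidence is high that the wording differs and moderate that the difference would change what a site does. Severity is minor.

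Its size for an affected subject is up to about 84 days of further dosing (70 to 98 with the windows) before the next scheduled ECG. This assumes that the finding arises at Week 12, is confirmed, is judged unrelated, and drug is continued.

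How often this would happen cannot be taken from the documents. Section 1.5 reports no clinically significant ECG abnormality in four trials in which 106 subjects received REN001, and a reader might turn 0 of 106 into a 95% upper limit of 1 − 0.05^(1/106) = 2.8%. That limit does not describe this case. It concerns any clinically significant abnormality and says nothing about relatedness. Three of the four trials were single-dose or lasted 28 days or less, and some enrolled healthy volunteers.

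Nor do the documents support any effect on power, Type 1 error or the primary estimate. Discontinuation of study drug is handled by a treatment policy strategy (Protocol Section 8.5.1, SAP Section 10.1.1).

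**What to change.** In Section 3.6 item 6, take the QTcF criterion out of the causality condition. The item could begin: *Confirmed post-baseline QTcF ≥ 500 msec (study drug is stopped as in Section 7.1.8, whatever the assessed causality), or other* and then continue with the present treatment-related wording for ECG changes, with its QTcF clause removed. The parenthesis makes the stop firm despite the permissive lead-in. Keep the repeat-ECG and monitoring text in item 6 and the physician over-read in Section 7.1.8 as they are.

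Restart needs no new text. Section 3.9 already says that for subjects who miss doses "due to an AE not related to study drug, they may be allowed to restart dosing after discussion" between the Investigator, Medical Monitor and Sponsor. Causality then bears on restart and no longer on the stop.

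The cost is one sentence, by amendment or clarification letter, with no new visit or procedure. A few subjects whose prolongation has another cause may stop drug, at least for a time. This is firmer than the liver and kidney rules, where discontinuation is only to be considered, but it follows what Section 7.1.8 already says on its face. Subjects who discontinue drug are asked to have an Early Termination visit, which includes an ECG when done at the center (Section 6.8), and "they will be strongly encouraged to continue in the study for their Week 12 and Week 24 visits" (Section 6.9). Walk data from those who attend are used under the treatment policy estimand. The minimum off-drug assessments in Section 6.9 include no ECG, which is why the monitoring requirement in item 6 must stay.

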3.7 Strategy for Potential Withdrawal due to Laboratory Test Abnormalities

[figure not shown]
3.7.1 Safety Monitoring for Serum Creatine Phosphokinase

Patients with PMM often present with mild to moderate baseline elevations in CK and can experience transient episodes of significantly elevated CK induced by vigorous exercise, and other environmental conditions. These elevations are not associated with symptoms or signs and the patients are typically well. CK elevations are generally of the skeletal muscle fraction. However, a small proportion of the total CK may be from the myocardial fraction reflecting a small amount of this fraction found in skeletal muscle rather than the presence of myocardial injury. Importantly, these elevations are entirely to be expected in this patient population with underlying muscle disease and are not synonymous with rhabdomyolysis. Similarly, elevations in serum aminotransferases and uric acid can accompany CK elevations and may not be indicative of liver disease.

True rhabdomyolysis may also occur in these patients and must be managed appropriately. Rhabdomyolysis is characterized by severe acute muscle injury resulting in muscle pain, weakness, and/or swelling with release of myofiber contents into the bloodstream. Symptoms develop over hours to days following an inciting factor and may be associated with dark pigmentation of the urine (Nance & Mammen, 2015). Acute kidney injury is a potential

complication of rhabdomyolysis. The risk of acute kidney injury is low in patients with CK levels less than 15,000 international units per liter (IU/L). The CK algorithm below (Figure 4) has been designed to identify those subjects potentially at risk of true rhabdomyolysis and ensure appropriate early action is taken to monitor and treat the subjects accordingly.

Figure 4: CK Algorithm

3.7.2 Safety Monitoring For Liver toxicity: Management and Stopping Rules

In this study, subjects with significant liver disease or impairment of AST or ALT >2.5 x ULN, or total bilirubin >1.6 x ULN or >ULN with other signs and symptoms of hepatotoxicity at Screening will be excluded. It would be inappropriate to exclude all subjects with milder elevations in LFTs out of the normal range because patients with PMM can present with elevations in CK levels that are often accompanied by elevated LFTs (ALT and AST), which are not indicative of liver disease. Accordingly, these elevations appear to be transient and resolve spontaneously (Tarnopolsky 2016). Although serum ALT and AST

values have shown good diagnostic accuracy in patients with chronic liver disease, AST and ALT levels can be increased immediately after muscular exertion as well ([Lippi 2008](#)).

In the event that a subject presents with raised LFTs during the study the following management guidelines and stopping rules should be followed:

- For subjects who enroll with a baseline below the ULN and present with an increase in serum ALT or AST > 3xULN, repeat testing of ALT, AST, ALP and total bilirubin will be obtained as soon as possible, ideally within 48-72 hours, to confirm the abnormality and whether the abnormality is increasing or decreasing.
- For subjects who enroll with a baseline above the ULN and present with an increase in serum ALT or AST > 3xULN and at least 2x their Baseline value, repeat testing of ALT, AST, ALP and total bilirubin will be obtained as soon as possible, ideally within 48-72 hours, to confirm the abnormality and whether the abnormality is increasing or decreasing.
- If symptoms persist or repeat testing shows ALT > 3xULN for subjects with normal baseline measures or 2x their Baseline value for subjects with elevated values at Baseline, initiate close observation with repeat testing 2-3 times weekly, or as clinically mandated, to determine whether the abnormalities are improving or worsening (see below for further details).
- If close monitoring is not possible, as a precautionary measure study drug should be withheld and continued participation in the study should be discussed with the Medical Monitor (See also [Section 6.9](#)).

Guidelines for Close Observation:

- Repeated ALT, AST, ALP, and total bilirubin tests two or three times weekly.
- Frequency of re-testing can decrease to once a week or less if abnormalities stabilize or the study drug has been discontinued and the subject is asymptomatic.
- Obtain a more detailed history of symptoms and prior or concurrent diseases.
- Recheck history of concomitant drug use (including non-prescription medications and herbal and dietary supplement preparations), alcohol use, recreational drug use, and any special diets.
- Rule out acute viral hepatitis types A, B, C, D, and E; autoimmune or alcoholic hepatitis; Non-alcoholic steatohepatitis (NASH); hypoxic/ischemic hepatopathy; and biliary tract disease.
- Obtain a history of exposure to environmental chemical agents.
- Obtain additional tests to evaluate liver function, as appropriate (e.g., International normalized ratio (INR) or Prothrombin time (PT), direct bilirubin).
- Consider gastroenterology or hepatology consultations.

Discontinuation:

Discontinuation or interruption of study drug should be considered, in consultation with the Medical Monitor and Reneo CMO or designee where possible, if:

- ALT or AST > 8xULN.
- ALT or AST > 5xULN for more than 2 weeks.
- ALT or AST > 3xULN and total bilirubin > 2xULN or INR >1.5.
- ALT or AST > 3xULN with the appearance of fatigue, nausea, vomiting, right upper quadrant pain or tenderness, fever, rash, and/or eosinophilia (>5%).

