3.7.3 Safety Monitoring For Kidney toxicity: Management and Stopping Rules

If subjects develop a creatinine elevation > 2xULN and more than 2x Baseline value:

- Monitor creatinine 2 times per week, or as clinically indicated, until recovery.
- For subjects with > 3xULN creatinine elevation the study drug should be withheld and the subject should continue to be followed closely.
- In the event of either of the above continued participation in the study should be discussed with the Medical Monitor.

Discontinuation:

Discontinuation of study drug should be considered, in consultation with the Medical Monitor and Reneo CMO or designee where possible, if:

- A > 3xULN creatinine elevation is sustained or deteriorating.
- The subject is unwell and has hyperkalemia.

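### Protocol 3.7.2 starts close liver observation on ALT alone, so a confirmed isolated AST rise in an asymptomatic subject with normal baseline gets one repeat panel and no required serial testing

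*Protocol*

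**What the plan says.** Section 3.7.2 works in three steps.

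- **Retest.** If baseline is below the ULN, a rise in ALT or AST above 3xULN calls for a repeat of ALT, AST, ALP and total bilirubin, ideally within 48 to 72 hours. If baseline is above the ULN, the subject must "present with an increase in serum ALT or AST > 3xULN and at least 2x their Baseline value".
- **Close observation.** This starts "If symptoms persist or repeat testing shows ALT > 3xULN for subjects with normal baseline measures or 2x their Baseline value", the last limb being for subjects whose values were elevated at Baseline. The guidelines for this step then call for "Repeated ALT, AST, ALP, and total bilirubin tests two or three times weekly". Sites may vary the frequency as clinically mandated, and "Frequency of re-testing can decrease to once a week or less if abnormalities stabilize". A work-up is listed here too: history, exclusion of viral and other hepatitis and of biliary disease, further liver function tests as appropriate, and consideration of specialist consultation. If close monitoring is not possible, study drug should be withheld as a precaution.
- **Discontinuation or interruption**, to be considered with the Medical Monitor. All four criteria name ALT or AST. One is "ALT or AST > 5xULN for more than 2 weeks"; another is "ALT or AST > 3xULN and total bilirubin > 2xULN or INR >1.5". The other two are a value above 8xULN, and a value above 3xULN with listed symptoms.

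The neighbouring kidney rule in Section 3.7.3 sets a default interval: "Monitor creatinine 2 times per week, or as clinically indicated, until recovery".

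**The concern.** AST counts when a rise is first noticed, is measured during close observation, and counts when stopping drug is considered. It is absent only from the trigger that links these steps. The protocol gives no reason. Where it discusses muscle-derived rises it treats the enzymes alike, referring to "elevations in CK levels that are often accompanied by elevated LFTs (ALT and AST"), so the text does not present AST as the one to discount.

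At stake is whether the plan's own rules can be applied. Close observation exists to show whether a rise is improving or worsening, and one discontinuation criterion needs values over more than two weeks. A subject whose only abnormality is AST is not required to have those values, nor the associated work-up. This is a patient-safety and consistency point; no effect on the efficacy analysis is claimed.

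**Working it through.** There is no figure in the plan to reproduce. The check is a trace through Section 3.7.2, then a count of days from Table 2.

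**Trace.** Subject with normal baseline, no symptoms, AST above 5 and up to 8xULN on the first and repeat tests, ALT at or below 3xULN, and no bilirubin or INR criterion met.

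| Step in 3.7.2 | Enzyme named | Result for this subject |
|---|---|---|
| Retest, baseline below ULN | ALT or AST | Met: one repeat panel |
| Start of close observation | ALT, or persisting symptoms | Not met |
| Close-observation panel and work-up | Panel includes AST | Not reached |
| Withhold drug if close monitoring not possible | Follows from close observation | Not reached |
| Above 8xULN | ALT or AST | Not met |
| Above 5xULN for more than 2 weeks | ALT or AST | Depends on later values that 3.7.2 does not order |
| Above 3xULN with bilirubin or INR | ALT or AST | Not met |
| Above 3xULN with listed symptoms | ALT or AST | Not met |

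The first two rows read the same for AST above 3 and up to 5xULN, so serial testing is not required there either. The two-week criterion is not in play in that range.

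**Days to the next required value.** Safety laboratory days with windows (Table 2): Week 2 = 11–17, Week 4 = 25–31, Week 12 = 77–91, Week 18 = 119–133, Week 24 = 161–175. Shortest gap = earliest later day minus latest earlier day; longest gap is the reverse. The repeat is assumed to be 2 to 3 days after the first value, following the 48 to 72 hour target.

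| Rise first seen | Next scheduled | Nominal gap | Gap with windows | From repeat, nominal | From repeat, with windows |
|---|---|---|---|---|---|
| Week 4 | Week 12 | 84 − 28 = 56 | 77 − 31 = 46 to 91 − 25 = 66 | 53–54 | 46 − 3 = 43 to 66 − 2 = 64 |
| Week 12 | Week 18 | 126 − 84 = 42 | 119 − 91 = 28 to 133 − 77 = 56 | 39–40 | 28 − 3 = 25 to 56 − 2 = 54 |
| Week 18 | Week 24 | 168 − 126 = 42 | 161 − 133 = 28 to 175 − 119 = 56 | 39–40 | 25 to 54 |

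The criterion turns on 14 days. For a rise first seen at Week 4, 12 or 18, the liver rules and the visit schedule together give values at day 0 and at day 2 or 3, and then none until day 28 at the earliest. A rise first seen at Week 2 is the exception: Week 4 is nominally 14 days later (25 − 17 = 8 to 31 − 11 = 20).

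**What close observation would supply.** Two to three tests a week give 2 × 2 = 4 to 2 × 3 = 6 values in 14 days, or 2 + 1 = 3 to 3 + 1 = 4 if testing steps down to weekly in the second week.

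**Raised baselines.** The limb on twice the Baseline value names no enzyme. Read on from the words before it, it means ALT; read against the retest bullet for raised baselines, a site could take it as either. The gap is unambiguous only for normal baselines.

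**The case against.** The strongest reply is that these subjects are not left without follow-up. The Medical Monitor and site physicians review data as they arrive (Section 1.4), and tests may be repeated if necessary (7.1.2). A change judged beyond normal physiologic fluctuation counts as clinically significant and hence as an adverse event (7.1.1.2). Adverse events must be followed until values return to baseline, stabilize acceptably or are explained (7.1.1.8.2, 7.1.1.11). A confirmed AST above 5xULN from a normal baseline would readily qualify. This stands as mitigation. But it rests on the investigator's judgment, and none of these sections sets a testing interval.

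The ALT-only trigger could also be deliberate, since AST is often of muscle origin in this disease, and the CK algorithm may add its own tests. Section 3.7.1 describes that algorithm as a tool for finding subjects at risk of rhabdomyolysis and ensuring they are monitored. Figure 4 is not reproduced in the text available, so this cannot be settled. A deliberate exclusion would still sit oddly with AST in every discontinuation criterion.

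The group is narrow. Above 8xULN one value suffices, and symptoms are not defined in the close-observation bullet. In a population entered for exercise intolerance or active muscle pain, some sites may start close observation on symptoms alone. The rules are also guidelines: discontinuation is to be considered, not imposed.

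A reader might infer that the protocol leaves AST rises unmonitored, or that AST cannot lead to stopping drug. Neither follows. Scheduled tests and adverse-event follow-up continue, and AST is in all four stopping criteria.

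A reader might also want a further rule for raised baselines, because bilirubin above 2xULN with AST or ALT above 3xULN can occur below the retest trigger (with baseline 2.5xULN that trigger is 2 × 2.5 = 5xULN). Such a subject already meets a discontinuation-consideration criterion with Medical Monitor consultation, so an added rule would gain little.

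**Conclusion.** The inconsistency is real and small. For a normal-baseline, asymptomatic subject with a confirmed AST above 3xULN and ALT at or below 3xULN, the liver rules require no serial testing after one repeat panel. For raised baselines the text is ambiguous.

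The practical consequence is concentrated in AST above 5 and up to 8xULN with no bilirubin, INR or symptom criterion met. After Week 4, the two-week criterion cannot be timed from tests that the liver rules require: the next scheduled value is nominally 39 to 54 days after the repeat, 25 to 64 with windows.

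This assumes a repeat at 2 to 3 days, visits within their windows, and no unscheduled tests. It is a statement about the liver rules in Section 3.7.2, not about all monitoring in the trial, because the CK algorithm could not be checked. The documents give no frequency for such rises, so the number of subjects affected is unknown. I rate it a cheap improvement, with medium confidence.

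**What to change.** In the close-observation bullet of Section 3.7.2, replace ALT with ALT or AST, and state that the limb on twice the Baseline value applies to either enzyme. Keep the allowance to test as clinically mandated, the step-down in frequency, and all discontinuation thresholds. If an ALT-only trigger was intended, one sentence of rationale should say so and explain how the two-week AST criterion is to be assessed.

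The drafting cost is one bullet, by site clarification letter or the next amendment. The operating cost is more than blood tests. Subjects brought in would also get the close-observation work-up, and drug might be withheld as a precaution where close monitoring is not possible. Some of these rises will be benign and muscle-derived. Section 1.4 allows that REN001 itself may cause transient benign muscle enzyme rises through increased muscle use, so the burden could fall more on the active arm. The step-down limits the testing part of this. The change helps this trial only while subjects are still on treatment, and the documents do not say how many are.
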